#### 3.7.2.5 Analyses for Week 36 Primary Efficacy Endpoints (MRI-PDFF)

Analyses of hepatic fat fraction from Baseline to Week 36 will follow the same analysis as Week 12, based on the mITT population. This analysis will also be repeated for the 36-Week Per Protocol Population. If there are patients who early withdraw between Weeks 12 and 36, then the following two analyses will be conducted:

- Analyze the primary endpoint (percent or absolute changes in hepatic fat fraction by MRI-PDFF) without the early withdrawals, that is, only include patients who finish Week 36 MRI-PDFF (mITT Population – Observed); and
- Last observation carried forward between Weeks 12 and 36, and use this last observation as the Week 36 value for the analysis (mITT Population – LOCF).

The percent and absolute change in hepatic fat fraction by MRI-PDFF between Week 12 and Week 36 without the early withdrawals will be analyzed, that is, only include patients who finish Week 36 MRI-PDFF. The results between Weeks 12 and 36 will show durability of response and whether MRI-PDFF at week 12 is a good a predictor of response or Week 36 is better.

Additional sensitivity analysis may be performed with other statistical models, such as Mixed effect Model Repeat Measurement (MMRM) method.

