10 STATISTICS

10.1 Analysis Populations

The Intent-to-Treat (ITT) Population will include all patients who are randomized in the study and receive at least 1 dose of study drug. The ITT Population will be used for all efficacy analyses.

The Per Protocol Population will include all ITT patients who finish the Week 12 visit with valid MRI-PDFF measurements and do not have any major protocol deviations. Patients who are <80% compliant over the course of the initial 12-week Treatment Period will not be included in the Per Protocol Population.

The Safety Population will include all patients who are randomized in the study and receive at least 1 dose of study drug and will be used for all safety analyses.

Demographics, disposition, and study populations will be summarized descriptively.

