10.2 Statistical Methods

10.2.1 Analysis of Efficacy

10.2.1.1 Primary efficacy analysis

The primary efficacy variable will be the percent change in MRI-PDFF from baseline to Week 12. Summary statistics (number of patients, mean, standard deviation, median, minimum, and maximum) at all visits and change from baseline will be provided. The primary efficacy analysis will be analyzed with an analysis of covariance (ANCOVA) model with treatment as a factor. For any patients in the ITT Population with a missing primary efficacy parameter, the control (placebo)-based pattern mixture model will be used. Based on PK obtained in healthy volunteers dosed for up to two weeks on doses of MGL-3196 from 20-200 mg per day, a significant fraction of patients randomized to an 80 mg dose may have their dose reduced to 60 mg after PK assessment at Week 2. The multiplicity (MGL-3196 60 mg versus placebo and MGL-3196 80 mg versus placebo) will be controlled by Dunnett's Test. The primary efficacy analysis will be performed based on the ITT Population and repeated based on the Per Protocol Population.

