#### **3.2.2 Modified Intent-to Treat Population**

The modified intent-to-treat (mITT) population includes all patients who were randomized in the study, received at least 1 dose of study drug, and had lipid and other efficacy measurements at Week 4 or later visits. The mITT population will be used for all secondary efficacy analyses.

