### 3.7.4.2 Lipid Measurements

All lipid measurements will be summarized by visit, as well as absolute and percent change from baseline to each post-baseline visit.

The same ANCOVA model as primary efficacy analysis will be used for analyzing the percent change and change:

- From baseline to Week 4,
- From baseline to Week 12 with LOCF (after Day 1 and up to Week 12),
- From baseline to Week 30 with LOCF (after Week 12 and up to Week 30),
- From baseline to Week 36 with LOCF (after Week 12 and up to Week 36),
- Average between Week 30 and Week 36, and
- Average between Week 16 and Week 36

for direct LDL-C, triglycerides, Lp(a), HDL, Non-HDL, Total Cholesterol, Apo C-III (after Week 12 only), and Apo B.

Lp(a) will be analyzed separately for baseline value  $\leq 10$  nmol/L and baseline value  $> 10$  nmol/L. In the ANCOVA model for change from baseline, baseline value will be included as a covariate. But the covariate of baseline value will not be included in the model for the analysis of percent change from baseline.

If skewness from normality is observed for triglycerides data, then the triglycerides value will be logarithm-transformed before fitting the ANCOVA model. The treatment difference between two visits will then be transformed back as the percent change from. If the normality assumption still can't be satisfied with the logarithm-transformed data, a non-parametric approach (Wilcoxon rank-sum test) will be used to compare the difference in median TG change or percent change between treatment groups.

A logistic regression model with treatment as a factor and baseline as a covariate may be used to compare the percentages of patients who achieve a change from baseline to endpoint in Lp(a) ( $\leq 10$  nmol/L vs.  $> 10$  nmol/L) between the MGL-3196 dose versus placebo. The odds ratio, confidence interval, and p-value will be provided.

Analyses of lipids may be performed for the following subgroups:

- Week 12 SHBG group ( $\geq 75\%$ ,  $< 75\%$  change from baseline to Week 12) for men and women separately;
- Week 36 SHBG group ( $\geq 88\%$ ,  $< 88\%$  change from baseline to mean SHBG post Week 12 through Week 36);
- Exposure group (AUC  $< 2700$  ng\*hr/mL, AUC  $\geq 2700$  ng\*hr/mL);
- Baseline Direct LDL Category ( $< 100$  mg/dL,  $\geq 100$  mg/dL);
- Baseline Triglycerides Category ( $\leq 150$  mg/dL,  $> 150$  mg/dL); and
- Any other data driven groups.

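### For withdrawals after Week 12, the Week 36 MRI-PDFF comparison is firmly planned only as completers-only and LOCF analyses, with no main analysis and nothing that counts loss of effect after stopping

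*SAP*

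**What the plan says.** SAP 3.7.2.5 sets the Week 36 MRI-PDFF analysis on the mITT population, with a repeat in the 36-Week Per Protocol Population. If patients withdraw between Weeks 12 and 36, two analyses are firm:

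- Completers: "only include patients who finish Week 36 MRI-PDFF (mITT Population – Observed").
- LOCF: "Last observation carried forward between Weeks 12 and 36, and use this last observation as the Week 36 value for the analysis".

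The section does not say which is the main one. It then adds: "Additional sensitivity analysis may be performed with other statistical models, such as Mixed effect Model Repeat Measurement (MMRM) method".

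The same section has a separate analysis of change from Week 12 to Week 36, meant to show durability. It includes only patients with a Week 36 scan, so no carried value enters it.

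Other text that bears on the point:

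- Protocol 10.2.1.1 says that for a missing primary efficacy parameter "the control (placebo)-based pattern mixture model will be used". The body of the SAP has no such model, although SAP Section 6 still lists pattern-mixture references.
- SAP 3.1 accepts MRI-PDFF scans up to three weeks after the last dose.
- Protocol 6.6 and 9.14 schedule a scan at early termination, but 6.6 leaves some procedures to discretion.
- SAP 3.2.2 admits to mITT patients who "had lipid and other efficacy measurements at Week 4 or later visits". A patient can therefore be in mITT without any scan from Week 12 on.
- Protocol Section 7 lists Week 36 percent change in MRI-PDFF as a secondary efficacy variable.

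**The concern.** Two different things can go wrong when patients leave after Week 12, and neither firm analysis deals with both.

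First, withdrawal may depend on how the patient was doing at Week 12. The percent-change model in SAP 3.7.2.1 contains treatment alone. The completers analysis therefore ignores the Week 12 scan of those who left, and if poor responders leave the active arm, the rest look better. LOCF uses that scan but assumes the patient stood still for up to 24 weeks.

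Second, a patient who stops drug may lose the effect. The carried scan is at most three weeks off drug, so LOCF enters a mostly on-drug value as a measured Week 36 result. Completers-only leaves the patient out. Neither counts the loss.

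With no estimand stated and no main analysis named, two estimates can be reported that differ for reasons the plan gives no basis to resolve. At stake is the size of the Week 36 liver-fat effect.

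**Working it through.** **Inputs from the documents.** Planned difference -30 points and SD 35 for percent change at Week 12; 36 completers per group; significance level 0.025 (SAP Section 4). Paired baseline and Week 12 scans: 78 active and 38 placebo (protocol, summary of Amendment 6 changes).

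**Assumptions, not in the documents.** Withdrawal share after Week 12, d = 5, 10 or 20%. Share of effect lost off drug, r. The -30 applies at Week 36. Week 12 to Week 36 correlation 0.7. Mean placebo change zero.

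**1. The plan's own figure.** A two-sample t-test with 36 per group, difference 30, SD 35 and two-sided 0.025 has 90.8% power, against a stated 90%. It reproduces. The documents give no power figure for Week 36.

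**2. Withdrawal that depends on Week 12 response.** Let all active withdrawals come from the poorest-responding third, and let placebo withdrawals be random. The top third of a normal distribution has mean 1.091 SD above centre.

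- Week 12 shift of those who leave: 1.091 x 35 = 38.2 points above the arm mean.
- Their expected Week 36 shift had they stayed on drug: 0.7 x 38.2 = 26.7.
- Completers estimate: -30 - d x 26.7 / (1 - d).
- LOCF estimate: -30 + d x (38.2 - 26.7).

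| d | True on-drug difference | Completers | LOCF |
|---|---|---|---|
| 5% | -30 | -31.4 | -29.4 |
| 10% | -30 | -33.0 | -28.9 |
| 20% | -30 | -36.7 | -27.7 |

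Simulating the 20% case (78 versus 38) gave -36.7 for completers, -27.6 for LOCF and -29.9 for a missing-at-random likelihood estimate, which is what an MMRM targets. Here the two firm analyses sit 9 points apart, on either side of the truth. This is a deliberately strong pattern: with a milder dependence, similar in both arms, all three estimates stayed within about 0.3 of -30.

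**3. Loss of effect after stopping.** If withdrawn patients count at their off-drug value, the true difference is -30 x (1 - d x r). With withdrawal unrelated to response and no further growth in effect, LOCF stays at -30, so it overstates by d x r x 30.

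| d | True difference, full loss (r = 1) | Overstatement, r = 1 | Overstatement, r = 0.5 |
|---|---|---|---|
| 5% | -28.5 | 1.5 | 0.75 |
| 10% | -27.0 | 3.0 | 1.5 |
| 20% | -24.0 | 6.0 | 3.0 |

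Simulation (1,500 runs per setting, 78 versus 38, full loss, Monte Carlo error about 0.2) compared the methods:

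| d | LOCF | Completers | Missing-at-random (MMRM) | Control-based | Target |
|---|---|---|---|---|---|
| 10% | -30.0 | -30.0 | -30.0 | -27.1 | -27.1 |
| 20% | -30.0 | -29.9 | -30.0 | -23.9 | -23.9 |

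Only control-based imputation reaches this target. MMRM misses it by the same amount as the two firm analyses.

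**4. Direction.** Suppose the on-drug effect grows by 20% from Week 12 to Week 36, to -36. With d = 20%, LOCF gives 0.8 x (-36) + 0.2 x (-30) = -34.8. That understates the on-drug effect of -36 by 1.2, yet overstates the effect that counts loss, 0.8 x (-36) = -28.8, by 6.0. The sign of the LOCF error depends on the target, which the SAP does not state.

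**The case against.** The strongest reply is that LOCF is not the sole handling. An observed-case analysis stands beside it, a per-protocol repeat follows, and neither is called main. That is correct, and the point here is about the pair and the missing designation. An early-termination scan also softens the problem where it is done, but it is discretionary and counts only within three weeks of the last dose.

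Several stronger readings are tempting, and the documents do not support them:

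- *LOCF manufactures durability.* A reader might infer this because Week 36 is meant to show lasting response. The durability analysis proper, Week 12 to Week 36, takes only patients with a Week 36 scan and uses no carried value.
- *Making MMRM mandatory cures the off-drug problem.* It does not. Under missing at random, withdrawn patients are modelled as if they had stayed on drug. MMRM handles dropout related to observed Week 12 response, and that alone.
- *The SAP breaks a protocol commitment for Week 36.* Protocol 10.2.1.1 ties the pattern mixture model to the missing primary parameter, which is Week 12. Protocol 10.2.1.2 carries the ANCOVA model to secondary variables without mentioning imputation. The protocol is a precedent for the method, not a rule for Week 36.
- *The bias favours the drug.* LOCF can err either way, as step 4 shows.
- *The same remedy applies to lipids.* SAP 3.7.4.2 does plan "From baseline to Week 36 with LOCF (after Week 12 and up to Week 36"), but lipids are measured at many visits and under a different off-drug rule (one day after the last dose). A model on Weeks 12 and 36 does not transfer, and this point does not extend there.

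The objection that the size is unsupported also stands in part: every withdrawal share above is an assumption.

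**Conclusion.** The concern holds for the baseline-to-Week-36 MRI-PDFF comparison. The SAP names no estimand and no main analysis. Its two firm methods can each be biased under dropout that the Week 12 scan would explain, and neither counts loss of effect after stopping.

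The size cannot be fixed from the documents. Against an on-drug target, the two firm estimates could lie about 9 points apart at 20% withdrawal under strongly response-dependent dropout, or hardly differ under mild dependence. Against a target that counts loss after stopping, the overstatement is withdrawal share x share of effect lost x 30 points: 1.5, 3 or 6 points at 5, 10 or 20% with full loss. That rests on carrying the Week 12 planning effect to Week 36.

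Significance is less exposed than the estimate. At 78 versus 38 and two-sided 0.05, power falls from 99.0% at -30 to 97.2% at -27 and 93.0% at -24. The endpoint is secondary and the Week 12 primary result is unaffected. This is a worthwhile, inexpensive improvement and not a threat to the trial's main conclusion.

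**What to change.** In SAP 3.7.2.5:

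1. State the Week 36 estimand, including whether a patient who stops drug counts at the on-drug or the off-drug value.
2. Name one main analysis: an MMRM on Weeks 12 and 36 with treatment, visit, treatment-by-visit interaction and baseline PDFF. It uses the Week 12 scan of patients who later withdraw.
3. Require control-based multiple imputation as a sensitivity analysis, the approach the protocol already names for the missing primary parameter. This is the part that addresses loss of effect after stopping. If the estimand chosen in item 1 counts that loss, read the control-based result as the estimate closest to it.
4. Keep the completers-only and LOCF analyses, labelled as supportive.
5. Report by arm the number of withdrawals between Weeks 12 and 36, the number of carried scans with time since last dose, and the number of patients with no scan from Week 12 on, who have no value to carry.

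The cost is SAP wording and standard programming, with no new data. The interval may widen slightly: in the simulation with random 20% withdrawal, the standard deviation of the estimate was 7.7 for the missing-at-random analysis against 7.2 for LOCF, and lower than the 8.2 for completers.

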### 3.7.2.6 Subgroup Analyses for Week 36 Primary Efficacy Endpoints

The analyses of percent change and absolute change in hepatic fat fraction will be performed for the MRI-PDFF Evaluable population for the following subgroups:

- Week 36 SHBG group ( $\geq 88\%$ ,  $< 88\%$  change from baseline to mean SHBG post Week 12; and,
- Exposure group (AUC  $< 2700$  ng\*hr/mL, AUC  $\geq 2700$  ng\*hr/mL).

### 3.7.3 Analyses of Liver Biopsy Results

All endpoints will be summarized and analyzed based on the mITT population for MGL-3196 80 mg versus placebo. For liver biopsy, mITT includes only patients with both eligible baseline and Week 36 biopsies. Since this is for exploratory purpose, no multiplicity will be controlled.

Responder variables at Week 36 include:

- NASH Biopsy Responders:
  - The number and percentage of patients achieving a 1-point reduction in NAS;
  - the number and percentage of patients achieving a 2-point reduction in NAS at 36 weeks;
  - the number and percentage of patients achieving a 2-point reduction in NAS at 36 weeks; and either  $\geq 1$  point reduction in lobular inflammation or  $\geq 1$  point reduction in hepatocellular ballooning; and
  - the number and percentage of patients achieving a 2-point reduction in NAS at 36 weeks; and no worsening of fibrosis.
- NASH Component Responder definition (only requires one or more criteria):
  - reduction in hepatocellular steatosis; or
  - reduction in lobular inflammation; or
  - reduction in hepatocellular ballooning.
- Fibrosis Responders:
  - the number and percentage of patients achieving  $\geq 1$  stage reduction in fibrosis;
  - the number and percentage of patients achieving  $\geq 1$  stage reduction in fibrosis; and no worsening of NAS; and
  - the number and percentage of patients achieving  $\geq 2$  stage reduction in fibrosis.
- NASH Resolution Responder Definition (requires both criteria):
  - lobular inflammation = 0 or 1; and
  - hepatocellular ballooning = 0.

- NASH Resolution Responders with at least a 2-point reduction in NAS at Week 36.
- Other exploratory NASH Resolution Responders:

- The number and percentage of patients achieving a change in NASH diagnosis (ie, from definite NASH to not-NASH based on histology) from baseline to Week 36.

The definite NASH based on histology is specified as: fibrosis stage 1 to 3 and a NAS of  $\geq 4$  with at least a score of 1 in each of the following NAS components:

- Steatosis (scored 0 to 3),
- Ballooning degeneration (scored 0 to 2), and
- Lobular inflammation (scored 0 to 3).

Fisher's exact test will be used to compare the percentages between MGL-3196 80 mg versus placebo. Confidence intervals and p-values will also be provided.

NOTE:

- The analyses performed on the NASH Resolutions endpoint will exclude patients with  $>9.5\%$  weight loss from Screening to Week 36 (the percent change in body weight from Screening to Week 36 is  $>-9.5\%$ ), including the patients only as secondary analyses. Conversely, other liver biopsy and study endpoints will include the patients, excluding them only as secondary analyses.

Other liver biopsy variables include:

- The change in fibrosis stage from baseline at 36 weeks; as a continuous variable and descriptively by numbers and percentages of patients in which fibrosis stage improved, was unchanged or worsened, for exploratory purposes only
- The change in portal inflammation from baseline at 36 weeks; and
- The change in parameters of NASH liver biopsy (NAS) from baseline at 36 weeks. The NAS score will also be summarized descriptively as a continuous variable for exploratory purposes only.
- Correlation of reduction of liver fat on MRI-PDFF at 12 and 36 weeks with improvement or resolution of NASH on liver biopsy.

Analyses of liver biopsy data will be performed on the mITT population for the following subgroups:

- Week 36 SHBG group ( $\geq 88\%$ ,  $<88\%$  change from baseline to mean SHBG post Week 12 through Week 36);
- Exposure group (AUC  $<2700$  ng\*hr/mL, AUC  $\geq 2700$  ng\*hr/mL);
- Baseline Fibrosis Stage 2/3;

- Weight loss from Screening to Week 36 (<5% weight loss,  $\geq 5\%$  weight loss,  $< 7\%$  weight loss,  $\geq 7\%$  weight loss,  $> 9.5\%$  weight loss);
- Baseline MRI-PDFF  $\geq 20\%$ ;
- Gender (male, female);
- Ethnicity (Hispanic or Latino, Not Hispanic or Latino );
- Stage of NASH ( $\geq 5$ ,  $< 5$ );
- PNPLA3 SNP phenotype (Homozygous, Heterozygous, negative);
- Type 2 diabetes (yes or no);
- MGL-3196 treated patients who have 30% or more reduction in hepatic fat fraction by MRI-PDFF from baseline at Week 12 and 36, that is, the percent change from baseline to Week 12 and 36 is  $\leq -30\%$  versus all Placebo treated patients;
- MGL-3196 treated patients who have 5% or more absolute reduction in hepatic fat fraction by MRI-PDFF from baseline at Week 36, that is, the change from baseline to Week 12 is  $\leq -5\%$  in hepatic fat versus all Placebo treated patients;
- MGL-3196 treated patients who have 5% or less hepatic fat fraction by MRI-PDFF at Week 12 and 36, that is, the hepatic fat fraction measurement at Week 12 and 36 is  $\leq 5\%$  versus all Placebo treated patients; and
- Any other data driven groups.

Other potential subgroups may be explored if any imbalance exists between treatment groups. Imbalance will be assessed using a chi-square test for categorical data, and an analysis of variance (ANOVA) will be used to test the imbalance for quantitative data.

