 - o Previous liver biopsy consistent with NASH.

Note: Assessment of the above, or other objective modalities suggested by PI, will occur. The choice of additional procedures, performed during the screening period prior to the screening MRI and liver biopsy, may include calculation of FIB-4, APRI, NAFLD fibrosis scores, and/or performance of fibroscan and/or CAP.

5. Must have confirmation of $\geq 10\%$ liver fat content on MRI-PDFF;

Note: Patients with a liver fat content $>9\%$ but $< 10\%$ on MRI-PDFF and who are highly likely to have NASH as determined by Medical Monitors on biopsy may be included in the study but the total may not exceed 10% of the total study population;

6. Biopsy-proven NASH:

- Must have had prior liver biopsy within 180 days of randomization with fibrosis stage 1 to 3 and a NAS of ≥ 4 with at least a score of 1 in each of the following NAS components:
 - Steatosis (scored 0 to 3),
 - Ballooning degeneration (scored 0 to 2), and
 - Lobular inflammation (scored 0 to 3); and

Note 1: Patients who have clear ballooning with fibrosis but no inflammation or patients who have clear inflammation with fibrosis but no ballooning or patients with clear NASH without fibrosis may be included in the study but the total may not exceed 10% of the total study population;

Note 2: If a historical biopsy is to be used, patients must have had no significant change in metabolic status (diabetes control, lipid metabolism, and/or $>5\%$ weight loss), significant change in diabetes medication, or change in use of medications listed in Exclusion #11 since the biopsy;

Note 3: If a historical biopsy is not available, patients must have confirmation of $\geq 10\%$ liver fat content on MRI-PDFF prior to undergoing liver biopsy. However, if, in the opinion of the patient's physician, the patient would benefit from and be advised to obtain a liver biopsy, the patient may undergo liver biopsy prior to MRI-PDFF;

7. Must have documented historical (3 weeks to 6 months prior to the study entry) ALT and AST levels consistent with the screening ALT and AST values. This consistency is established based on the following:

- If the historical and screening ALT and AST values are both $\leq 1.5 \times$ the upper limit of normal (ULN), there is no limit to the difference between the values

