### **3.2.4 Liver Biopsy Evaluable Population**

The liver biopsy evaluable population includes all patients who were randomized in the study, received study drug, with two valid evaluable liver biopsies, one at baseline and one post-treatment. In addition to the following per-protocol populations, additional analyses on the liver biopsy evaluable population will be performed using a Posthoc Per-Protocol Population, as warranted.

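### NASH resolution is judged on Week 36 scores alone, so any patient admitted under Note 1 with ballooning 0 and inflammation 1 would count as resolved on an unchanged biopsy

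*SAP*

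**What the plan says.** SAP 3.7.3 gives a "NASH Resolution Responder Definition (requires both criteria"), the two criteria being lobular inflammation 0 or 1 and ballooning 0. The list is headed as Week 36 responder variables. SAP 2.1.3 and 2.3.1.2 repeat the rule, and Protocol Section 7 uses the same two scores for its secondary variable. Protocol 2.2 places resolution under histological improvement relative to baseline.

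Inclusion #6 in Protocol 4.1 requires a NAS of 4 or more, fibrosis stage 1 to 3 and "at least a score of 1 in each of the following NAS components". Note 1 relaxes this for three patient types. One is ballooning without inflammation. The text continues: "patients who have clear inflammation with fibrosis but no ballooning or patients with clear NASH without fibrosis may be included in the study". The three types share one cap: they "may be included in the study but the total may not exceed 10% of the total study population".

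On the analysis set, SAP 3.7.3 states: "For liver biopsy, mITT includes only patients with both eligible baseline and Week 36 biopsies". SAP 3.2.4 asks only for patients "with two valid evaluable liver biopsies, one at baseline and one post-treatment". The one exclusion specific to resolution is weight loss above 9.5%. A separate endpoint counts "NASH Resolution Responders with at least a 2-point reduction in NAS at Week 36". On the status of all these analyses, SAP 3.7.3 says: "Since this is for exploratory purpose, no multiplicity will be controlled".

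**The concern.** A responder rule built on absolute end-of-study scores works only if nobody can satisfy it on entry. The main inclusion rule guarantees that; Note 1 does not. A patient with ballooning 0 and inflammation 1 at baseline who shows no change at Week 36 would be added to the resolved count. That contradicts an objective framed as improvement from baseline.

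What is at stake is the accuracy of one named secondary variable. Each such patient adds a response that treatment did not produce, in whichever arm the patient happens to be.

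**Working it through.** **1. Which entry states already meet the rule.** Ranges are from Inclusion #6: steatosis 0–3, ballooning 0–2, inflammation 0–3. I take steatosis as at least 1 throughout. Week 36 is set equal to baseline.

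| Entry route | Score states | Already resolved |
|---|---|---|
| Inclusion #6 in full (each component ≥ 1, NAS ≥ 4, stage 1–3) | 3×2×3×3 − 3 = 51 | 0 |
| Note 1: ballooning, no inflammation | 3×2×3 = 18 | 0 |
| Note 1: NASH without fibrosis (read as ballooning and inflammation both ≥ 1) | 3×2×3 = 18 | 0 |
| Note 1: inflammation, no ballooning | 3×3×3 = 27 | 9 (all with inflammation 1) |

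The first three rows give none because ballooning is at least 1. In the last row, inflammation 1 combines with 3 steatosis scores and 3 fibrosis stages: 3×3 = 9. If NAS ≥ 4 still applies to Note 1 patients, only steatosis/ballooning/inflammation 3/0/1 remains, since 3+0+1 = 4.

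**2. How many patients.** No count is given. The cap allows 0.10 × 117 = 11.7, so 11 of the planned patients, or 0.10 × 125 = 12.5, so 12 of the 125 in the safety table of the Amendment 6 summary. Either figure requires every Note 1 patient to be of this one kind.

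**3. Whether they are in the analysis set.** SAP 3.7.3 does not define an eligible baseline biopsy. A Note 1 patient is eligible under Inclusion #6, SAP 3.2.4 does not exclude one, and the weight-loss exclusion ignores baseline histology. Nothing in the visible text removes them.

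**4. Illustrative size.** The documents give no power statement for biopsy endpoints, so there is no planned figure to reproduce. My assumptions are 73 active and 35 placebo biopsy pairs, true resolution 20% vs 5%, two-sided α = 0.05, and affected patients who still meet the rule at Week 36. The weight-loss exclusion is not deducted.

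With k₁ and k₂ affected patients in the active and placebo arms, X = k₁ + Bin(73 − k₁, 0.20) and Y = k₂ + Bin(35 − k₂, 0.05). Power is the sum of P(X = x)·P(Y = y) over tables with Fisher p ≤ 0.05. It is averaged over the hypergeometric allocation of m affected patients among 73 + 35 = 108.

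For m = 1: (73/108)(0.538) + (35/108)(0.252) = 0.364 + 0.082 ≈ 0.445.

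The expected difference is 15 × (1 − m/108) points, because each affected patient adds on average 0.80/108 to the active rate and 0.95/108 to the placebo rate.

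| Affected patients m | Expected difference (points) | Power | Type I error (5% in both arms) |
|---|---|---|---|
| 0 | 15.0 | 48% | 0.022 |
| 1 | 14.9 | 45% | 0.024 |
| 2 | 14.7 | 42% | 0.025 |
| 3 | 14.6 | 39% | 0.026 |

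Removing the affected patients gives 47% (72 vs 35), 49% (73 vs 34) or 46% (71 vs 34).

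**5. Other assumed values.** Take 78 active and 38 placebo pairs (the Week 12 MRI-PDFF counts), with two affected patients in active and one in placebo. At 25% vs 5%, power is 77% with none affected, 71% as scored and 75% with them excluded. At 30% vs 10% the figures are 67%, 62% and 66%.

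**The case against.** The strongest reply is that the case is narrow and may be empty. It needs Note 1 entry, the no-ballooning type, and inflammation of exactly 1. Note 1 asks for clear inflammation without naming a score, so it is an inference that 1 qualifies. This stands, and it is why the point is conditional.

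The SAP also reports endpoints that an unchanged biopsy of this kind cannot meet: resolution with a 2-point NAS reduction, and the change from definite NASH, which requires baseline ballooning. That is true, but they are listed separately and leave the plain count as it is. The version history mentions the 2-point requirement under v1.1, yet the operative text keeps the two-criterion rule beside it. Some exploratory resolution definitions are blacked out. They may condition on baseline, and this cannot be checked.

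The rule originates in the protocol, so the SAP is following its source. That is correct, and it is a reason to add an analysis and leave the definition in place.

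A reader might go further in three ways, and the documents do not support any of them:

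- **That the rule favours the drug.** Allocation is random, so these patients are expected in proportion in both arms. The average effect is dilution. Chance imbalance could go either way.
- **That about 12 patients are affected.** That is a ceiling. Three patient types share the cap, and no count is reported.
- **That one patient can halve the power.** The 25% figure arises only if the single affected patient is in placebo; one in active gives 54%. The average is 45%.

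**Conclusion.** The point holds as a minor one. The plain resolution rule can count an unchanged biopsy as a response, for one Note 1 patient type with inflammation 1, if any were enrolled and are in the biopsy set. No visible passage prevents this.

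On the assumed 73/35 split and 20% vs 5% rates, one to three such patients cost about 3 to 9 points of power on average and less than half a point of expected difference. Type I error averaged over allocation stays near 0.025. These figures rest on assumed biopsy counts, response rates and α, and on affected patients staying unchanged on the two resolution components. The primary MRI-PDFF endpoint is not touched, and the biopsy analyses are labelled exploratory without multiplicity control.

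**What to change.** In SAP 2.1.3, 2.3.1.2 and 3.7.3, add an analysis of NASH resolution restricted to patients who do not already meet both criteria at baseline. List those excluded by arm, and report the result beside the protocol-defined rate in all patients. State that Note 1 patients have an eligible baseline biopsy and stay in the all-patient version.

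SAP 2.2.1 says the treatment code was revealed while the extension was running. If the addition is made after that, keep the protocol definition as the main version and label the restricted one a post-unblinding sensitivity analysis.

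The cost is one sentence in each of three sections, one listing and one table row. The drawback is that the restricted version departs from the protocol variable, so it must not replace it. If the listing is empty, the question is closed.
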